## 6.4. Replacement of unusable vaccine doses

In addition to the vaccine doses provided for the planned number of subjects (including over-randomization when applicable), at least 10% additional vaccine doses will be supplied to replace those that are unusable.

## 6.5. Contraindications to subsequent vaccination

The following events constitute absolute contraindications to further administration of MenABCWY, rMenB+OMV NZ, or MenACWY. If any of these events occur during the study, the subject must not receive additional doses of vaccine(s) but may continue other study procedures at the discretion of the investigator (see Section 8.5).

- Anaphylaxis following the administration of vaccine(s).
- Pregnancy (see Section 8.2.1).
- Any occurrence of an event listed in the exclusion criteria, which must always be re-assessed by the investigator before administration of the second dose of study vaccine(s). Refer to Section 4.3.
- Subjects who experience any SAE judged to be possibly or probably related to study vaccine(s), including hypersensitivity reactions.
- Subjects who develop any new condition which, in the opinion of the investigator, may pose additional risk to the subject if he/she continues to participate in the study.
- Any condition that in the judgment of the investigator would make IM injection unsafe.

The following events constitute contraindications to administration of MenABCWY, rMenB+OMV NZ, or MenACWY at that point in time; if any of these events occur at the time scheduled for vaccination, the subject may be vaccinated at a later date, within the time window specified in the protocol (see Section 5.5).

- Body temperature elevation (i.e. fever) within 3 days prior to intended study vaccination. Fever is defined as temperature  $\geq 38.0^{\circ}\text{C}$ .
- Significant acute illness (e.g. acute severe febrile illness) within 7 days prior to vaccination.
- Administration of any other vaccine 14 days (for inactivated vaccines), 28 days (for live vaccines), or 7 days (for influenza vaccines) prior to vaccination.

Additionally, the following event warrants the delay of blood sample collection for immunogenicity assessments in this study.

- Receipt of systemic antibiotics with the previous 3 days before blood sample collection.

In the event that a subject meets the criterion for delay of blood sample collection, blood sample collection may proceed once the appropriate window for delay has passed.

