16. Any confirmed or suspected immunosuppressive or immunodeficient condition, based on medical history and physical examination (no laboratory testing required).
17. Are obese at screening (e.g. with a body mass index [BMI]  $\geq 30 \text{ kg/m}^2$ , where BMI reflects obesity and not high muscle mass).
18. Family history of congenital or hereditary immunodeficiency.
19. History of neuroinflammatory or autoimmune condition.
20. History of significant neurological disorder or seizure (history of febrile convulsion should not lead to exclusion).
21. Serious chronic illness.
22. History of chronic alcohol consumption and/or drug abuse (including current consumption/abuse).
23. Any study personnel as an immediate family or household member.

24. Administration of a vaccine not foreseen by the study protocol in the period starting 14 days (for inactivated vaccines), 28 days (for live vaccines), or 7 days (for influenza vaccines) before each dose and ending 14 days (for inactivated vaccines), 28 days (for live vaccines), or 7 days (for influenza vaccines) after each dose of study vaccine(s) administration.

25. Thrombocytopenia, bleeding disorders, or be receiving anticoagulant therapy.

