**Table 5 Intervals between study visits**

Interval	Optimal length of interval	Allowed interval (Min – Max) 
Visit 1 (Day 1) → Safety call 1 (Day 15)	14 days	11 days – 17 days (Days 12 – 18)
Visit 1 (Day 1) → Visit 2 (Day 31)	30 days	23 days – 40 days (Days 24 – 41)
Visit 1 (Day 1) → Visit 3 (Day 61)	60 days	53 days – 70 days (Days 54 – 71)
Visit 3 (Day 61) → Safety call 2 (Day 75)	14 days	11 days – 17 days (Days 72 – 78)
Visit 3 (Day 61) → Visit 4 (Day 91)	30 days	23 days – 40 days (Days 84 – 101)

Safety call time intervals will not be used for the assessment of protocol deviations. The Study Day ranges shown in the table are based on optimal intervals; the actual Study Day ranges for Safety Call 2 and Visit 4 will be based on when Visit 3 occurs.

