### 6.7.2. Concomitant medications/products/vaccines that may lead to the elimination of a subject from per-protocol analyses

The use of the following concomitant medications/products/vaccines will not require withdrawal of the subject from the study but may determine a subject's evaluability in the per-protocol analysis. See Section 10.5 for analyses sets to be analyzed.

- Any investigational or non-registered product (drug or vaccine) other than the study vaccine(s) used during the study period.
- Immunosuppressants or other immune-modifying drugs administered chronically (i.e. more than 14 consecutive days in total) during the study period. Inhaled and topical steroids are allowed.
- Long-acting immune-modifying drugs administered at any time during the study period (e.g. infliximab).
- A vaccine not foreseen by the study protocol administered during the period of 14 days (for inactivated vaccines), 28 days (for live vaccines), or 7 days (for influenza vaccines) before or after administration of the study vaccine(s) at Visit 1 and Visit 3\*.

\*In case an emergency mass vaccination for an unforeseen public health threat (e.g.: a pandemic) is organized by the public health authorities, outside the routine immunization program, the time period described above can be reduced if necessary for that vaccine provided it is licensed and used according to its SmPC and according to local governmental recommendations and provided a written approval of the sponsor is obtained.

- Drug and/or alcohol abuse that, in the opinion of the investigator, will interfere with the results of the study or pose additional risk to the subject.

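### Protocol Section 6.5 both bars and merely delays dose 2 for the same event, a non-study vaccine given shortly before it

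*Protocol*

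**What the plan says.** **Protocol 4.3, criterion 24.** A non-study vaccine is excluded in windows of 14, 28 or 7 days, by vaccine type, running "before each dose and ending 14 days (for inactivated vaccines), 28 days (for live vaccines), or 7 days (for influenza vaccines) after each dose". Section 4.3 says the criteria are checked at entry, but Table 4 schedules another eligibility check at Visit 3, the dose 2 visit.

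**Protocol 6.5, absolute list.** One entry is "Any occurrence of an event listed in the exclusion criteria, which must always be re-assessed by the investigator before administration of the second dose". The consequence for every entry on this list is that "the subject must not receive additional doses of vaccine(s) but may continue other study procedures at the discretion of the investigator".

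**Protocol 6.5, temporary list.** One entry is "Administration of any other vaccine 14 days (for inactivated vaccines), 28 days (for live vaccines), or 7 days (for influenza vaccines) prior to vaccination". The consequence here is that "the subject may be vaccinated at a later date, within the time window specified in the protocol".

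**Protocol Table 5.** Visit 3 is due 60 days after Visit 1 (Day 61). The allowed interval is 53 to 70 days, that is Days 54 to 71.

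**Protocol 6.7.2 and SAP 5.2.** Section 6.7.2 lists the same vaccine windows around Visits 1 and 3 and says use of such products "will not require withdrawal of the subject from the study but may determine a subject's evaluability in the per-protocol analysis". SAP 5.2 lists the item as a key significant deviation, and significant deviations exclude the subject from the per-protocol sets. Both allow a shorter window for emergency mass vaccination with the sponsor's written approval.

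**The concern.** Criterion 24 is written for each dose, so a subject can meet it after enrolment. Section 6.5 then carries every exclusion criterion into the list that ends vaccination. A few lines later it names this same event, with the same windows, as a reason only to wait. Nothing says which list governs or exempts criterion 24 from the first one.

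Dose 2 defines the primary time point in four of the five groups, about 400 subjects. Two sites facing the same subject could act differently, and each could cite Section 6.5. A subject who is denied dose 2 does not complete the series and, under SAP 5.2, leaves the per-protocol sets for not having been vaccinated as planned. A subject who waits out the window and is dosed by Day 71 can stay in.

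Differences in handling would also be hard to see afterwards. The Visit 3 eligibility check needs no entry in the case report form (open circle in Table 4). The reasons for stopping study vaccine in Section 9.2.2 include no category for a contraindication or a prohibited vaccine, only a free-text other.

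**Working it through.** The plan states no figure on this point, so there is none to reproduce. The check sets the rules side by side and works out, by day of the non-study vaccine, which of them apply.

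**Inputs.** Dose 1 is on Day 1. Dose 2 is planned on Day 61 and allowed to Day 71 (Table 5). The window w is 14, 28 or 7 days (criterion 24 and Section 6.5). Let d be the study day of the non-study vaccine, from Day 2 to Day 60. I assume that w full days must pass, so dosing can resume on day d + w + 1.

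**Formulas.**
- Inside the window after dose 1: d - 1 ≤ w, so d runs from 2 to 1 + w.
- Inside the window before dose 2: 61 - d ≤ w, so d runs from 61 - w to 60.
- The wait still fits: d + w + 1 ≤ 71, so d ≤ 70 - w.

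| Type | w | After dose 1 only | Before dose 2, wait fits | Before dose 2, wait does not fit |
|---|---|---|---|---|
| Inactivated | 14 | Days 2-15 | Days 47-56 | Days 57-60 |
| Live | 28 | Days 2-29 | Days 33-42 | Days 43-60 |
| Influenza | 7 | Days 2-8 | Days 54-60 | none |

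For influenza, 70 - 7 = 63, so every day up to Day 60 fits. If dosing is allowed exactly on day d + w, the conflict begins one day later (61 - d < w) and the last day that fits becomes 71 - w (Day 57 inactivated, Day 43 live). A planned day other than Day 61 moves the start of the pre-dose window.

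**Before dose 2, wait fits.** The absolute list ends vaccination and the temporary list permits a later dose. If barred, the subject leaves PPS3. If delayed past the window and dosed by Day 71, the subject has neither a vaccine deviation at Visit 3 nor an out-of-window visit, and can remain. Here both dosing and PPS3 membership depend on the reading.

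**Before dose 2, wait does not fit.** The temporary list allows a later dose only within the visit window. Both lists therefore end without a permitted dose 2, and the outcome does not differ.

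**After dose 1 only.** The temporary list no longer applies by Day 61. Read literally, criterion 24 through the absolute list bars dose 2. SAP 5.2 removes these subjects from the per-protocol sets whether or not dose 2 is given, so the open question is dosing only.

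**Emergency mass vaccination.** Sections 6.7.2 and SAP 5.2 let the sponsor approve a shorter window. Criterion 24 and both lists of Section 6.5 have no such exception. A case approved for analysis purposes could still be barred from dose 2 by the absolute list.

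**The case against.** The best defence is that the lists can be read together. Criterion 24 is anchored to doses. If dose 2 is postponed until the window has passed, the vaccine no longer falls shortly before any dose given, so the pre-dose part of the criterion is never met. The temporary list names the event directly, whereas the absolute list reaches it only by cross-reference, and a specific rule would normally override a general one. Section 4.3 also places the criteria at study entry.

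That reading is possible, but neither it nor any order of precedence is written down. Section 6.5 and Table 4 both call for re-assessment at dose 2. Nor does it resolve a vaccine given soon after dose 1, which meets criterion 24 however long dose 2 is postponed.

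A reader might also infer that Section 6.7.2 is a third, contradictory instruction that lets the subject go on to dose 2. It is not. It speaks of withdrawal from the study, which Section 9.2.2 separates from withdrawal from study vaccine. It is silent on dose 2 and compatible with either list of Section 6.5.

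A further inference is that handling would differ between study groups. The rule text is the same for all four two-dose groups and the documents point to no mechanism for a group difference. Differences between sites are plausible in an open-label trial, but they are partly buffered because allocation is minimised on center and center is a term in the models.

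**Conclusion.** The conflict is real and lies within Section 6.5: the same vaccine, in the same pre-dose windows, both ends vaccination and only postpones it. A literal bar on dose 2 after a vaccine given soon after dose 1, and the missing emergency exception, add to it. PPS3 membership is affected only in the wait-fits column of the table, given a dose planned on Day 61 and a full window elapsed before dosing.

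The number of subjects cannot be derived from the documents. It is tempting to assume that 2% to 10% of about 400 subjects receive such a vaccine, which gives 8 to 40 (400 × 0.02 and 400 × 0.10). Losing all of them evenly would leave 98 to 90 per group and take power from the 79.6% in Protocol Table 14 to 79.0% or 76.4% (one-sided 10% t-test, difference -0.130, SD 0.435). This is at most an assumed upper bound. The rate has no source in the documents, and the sum counts subjects whose PPS3 status is the same under either reading. The point does not rest on it. The study is also exploratory with descriptive analyses, so what matters is consistent dosing and a clear rule for who is in the primary set.

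**What to change.** Reconcile criterion 24 with the two lists of Section 6.5 so that a non-study vaccine has one stated consequence for dose 2 in each of three cases: given before dose 2, given after dose 1, and given so late that the wait would pass the Table 5 limit. If the event is to stay in one list, exempt it from the other explicitly. Align Section 6.7.2 with the result, state whether its emergency mass-vaccination exception also governs dosing, and check that SAP 5.2 still matches. Which consequence applies in each case is for the sponsor's medical team to decide.

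The cost is wording in Protocol 4.3, 6.5 and 6.7.2 and a clarification letter to sites, with no extra visits or data.

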## 6.6. Warnings and precautions

Please also refer to the Investigator Brochure for MenABCWY. Please refer to the approved SmPCs for the commercial MenACWY and rMenB+OMV NZ vaccines.

## 6.7. Concomitant medications/products and concomitant vaccinations

At each study contact, the investigator or delegate should question the subject and/or the subject's parent(s)/LAR(s) about any medications/products taken and vaccinations received by the subject.

### 6.7.1. Recording of concomitant medications/products and concomitant vaccinations

The following concomitant medications/products and concomitant vaccines must be recorded in the subject records and the eCRF.

- All concomitant medications/products, except vitamins and dietary supplements, administered through 30 days post-vaccination.
- Any concomitant vaccination administered in the period starting 28 days before the first dose of study vaccine(s) and ending at the last study visit (Day -28 to Day 91).
- Prophylactic medication (i.e. medication administered in the absence of ANY symptom and in anticipation of a reaction to the vaccination).

For example, an antipyretic is considered to be prophylactic when it is given in the absence of fever and any other symptom, to prevent fever from occurring (fever is defined as temperature  $\geq 38.0^{\circ}\text{C}$  regardless the location of measurement). The preferred location for measuring temperature in this study is the axilla.

- Any concomitant medications/products/vaccines listed in Section 6.7.2.
- Any concomitant medications/products administered for treatment of an AE to be recorded as per protocol-specified reporting period (see [Table 11](#)).
- Any concomitant medications/products/vaccines relevant to an SAE/AESI to be reported as per protocol or administered at any time during the study period for the treatment of an SAE/AESI. In addition, concomitant medications relevant to SAEs and AESIs need to be recorded on the Expedited Adverse Events Report.
- The use of antipyretic and/or other medications to prevent (prophylactic use) and/or treat fever during the first 7 days after vaccination to be recorded in the eCRF as well.

### 6.7.2. Concomitant medications/products/vaccines that may lead to the elimination of a subject from per-protocol analyses

The use of the following concomitant medications/products/vaccines will not require withdrawal of the subject from the study but may determine a subject's evaluability in the per-protocol analysis. See Section 10.5 for analyses sets to be analyzed.

- Any investigational or non-registered product (drug or vaccine) other than the study vaccine(s) used during the study period.
- Immunosuppressants or other immune-modifying drugs administered chronically (i.e. more than 14 consecutive days in total) during the study period. Inhaled and topical steroids are allowed.
- Long-acting immune-modifying drugs administered at any time during the study period (e.g. infliximab).
- A vaccine not foreseen by the study protocol administered during the period of 14 days (for inactivated vaccines), 28 days (for live vaccines), or 7 days (for influenza vaccines) before or after administration of the study vaccine(s) at Visit 1 and Visit 3\*.

\*In case an emergency mass vaccination for an unforeseen public health threat (e.g.: a pandemic) is organized by the public health authorities, outside the routine immunization program, the time period described above can be reduced if necessary for that vaccine provided it is licensed and used according to its SmPC and according to local governmental recommendations and provided a written approval of the sponsor is obtained.

- Drug and/or alcohol abuse that, in the opinion of the investigator, will interfere with the results of the study or pose additional risk to the subject.

## **6.8. Intercurrent medical conditions that may lead to elimination of a subject from per-protocol analyses**

At each study visit/safety call subsequent to the first vaccination/the vaccination visit, it must be verified if the subject has experienced or is experiencing any intercurrent medical condition. If it is the case, the condition(s) must be recorded in the subject records and the eCRF.

Subjects may be eliminated from the per-protocol cohort for immunogenicity if, during the study, they incur a condition that has the capability of altering their immune response (i.e. human immunodeficiency virus or hematological malignancies) or are confirmed to have an alteration of their initial immune status.

For analysis purposes, intercurrent conditions will be identified using AEs reported in the eCRFs during the study.

## **7. HEALTH ECONOMICS**

Not applicable.

## **8. SAFETY**

The investigator or site staff is/are responsible for the detection, documentation and reporting of events meeting the criteria and definition of an AE or SAE as provided in this protocol.

Each subject/subject's parent(s)/LAR(s) will be instructed to contact the investigator immediately should they/the subject manifest any signs or symptoms they perceive as serious.

## **8.1. Safety definitions**

### **8.1.1. Definition of an adverse event**

An AE is any untoward medical occurrence in a clinical investigation subject, temporally associated with the use of a medicinal product, whether or not considered related to the medicinal product.

An AE can therefore be any unfavorable and unintended sign (including an abnormal laboratory finding), symptom, or disease (new or exacerbated) temporally associated with the use of a medicinal product. For marketed medicinal products, this also includes failure to produce expected benefits (i.e. lack of efficacy), abuse or misuse.

Examples of an AE include:

- Exacerbation of a chronic or intermittent pre-existing condition including either an increase in frequency and/or intensity of the condition.
- New conditions detected or diagnosed after study vaccine administration even though they may have been present prior to the start of the study.
- Signs, symptoms, or the clinical sequelae of a suspected interaction.
- Signs, symptoms, or the clinical sequelae of a suspected overdose of either study vaccine(s) or a concurrent medication (overdose per se should not be reported as an AE/SAE).
- Signs, symptoms temporally associated with study vaccine(s) administration.
- Pre- or post-treatment events that occur as a result of protocol-mandated procedures (i.e. invasive procedures, modification of subject's previous therapeutic regimen).

Adverse events to be recorded as endpoints (solicited AEs) are described in Section [8.1.3](#). All other AEs will be recorded as UNSOLICITED AEs.

Examples of an AE DO NOT include:

- Medical or surgical procedures (e.g. endoscopy, appendectomy); the condition that leads to the procedure is an AE/SAE.
- Situations where an untoward medical occurrence did not occur (e.g. social and/or convenience admission to a hospital, admission for routine examination).
- Anticipated day-to-day fluctuations of pre-existing disease(s) or condition(s) present or detected at the start of the study that do not worsen.
- Pre-existing conditions or signs and/or symptoms present in a subject prior to the first study vaccination. These events will be recorded in the medical history section of the eCRF.

**8.1.2. Definition of a serious adverse event**

An SAE is any untoward medical occurrence that:

- a. Results in death,
- b. Is life-threatening,

Note: The term “life-threatening” in the definition of “serious” refers to an event in which the subject was at risk of death at the time of the event. It does not refer to an event, which hypothetically might have caused death, had it been more severe.

- c. Requires hospitalization or prolongation of existing hospitalization,

Note: In general, hospitalization signifies that the subject has been admitted at the hospital or emergency ward for observation and/or treatment that would not have been appropriate in the physician’s office or in an out-patient setting. Complications that occur during hospitalization are also considered AEs. If a complication prolongs hospitalization or fulfills any other serious criteria, the event will also be considered serious. When in doubt as to whether “hospitalization” occurred or was necessary, the AE should be considered serious.

Hospitalization for elective treatment of a pre-existing condition (known or diagnosed prior to informed consent signature) that did not worsen from baseline is NOT considered an AE.

- d. Results in disability/incapacity, OR

Note: The term disability means a substantial disruption of a person’s ability to conduct normal life functions. This definition is not intended to include experiences of relatively minor medical significance such as uncomplicated headache, nausea, vomiting, diarrhea, influenza like illness, and accidental trauma (e.g. sprained ankle) which may interfere or prevent everyday life functions but do not constitute a substantial disruption.

- e. Is a congenital anomaly/birth defect in the offspring of a study subject.

Medical or scientific judgement should be exercised in deciding whether reporting is appropriate in other situations, such as important medical events that may not be immediately life-threatening or result in death or hospitalization but may jeopardize the subject or may require medical or surgical intervention to prevent one of the other outcomes listed in the above definition. These should also be considered serious.

Examples of such events are invasive or malignant cancers, intensive treatment in an emergency room or at home for allergic bronchospasm, blood dyscrasias, or convulsions that do not result in hospitalization.

